1.0 TRIAL SUMMARY

Abbreviated Title	Pembrolizumab and lenalidomide in Patients with Relapsed Refractory Non-Hodgkin and Hodgkin Lymphoma (HL)
Trial Phase	Phase I/II
Clinical Indication	Phase 1: Relapsed B cell HL and non-Hodgkin lymphoma (NHL); Phase 2: relapsed refractory (RR) HL
Trial Type	Therapeutic intervention
Type of control	n/a
Route of administration	Pembrolizumab IV; Lenalidomide PO
Trial Blinding	n/a
Treatment Groups	Phase 1: 9 patients expected (12 patients if unexpected toxicity) with relapsed HL and NHL Phase 2: 17 patients with RR HL
Number of trial subjects	26 (up to 29 if unexpected toxicity)
Estimated enrollment period	18-24 months
Estimated duration of trial	36-48 months
Duration of Participation	Until disease progression or toxicity up to 2 years

2.0 TRIAL DESIGN

2.1 Trial Design

This is a Phase 1/2 open label study of the combination of pembrolizumab and lenalidomide and in patients with relapsed/refractory (RR) non-Hodgkin lymphoma (NHL) and Hodgkin lymphoma (HL).

Dose escalation will follow a standard 3+3 design. Patients will be treated in cohorts of 3 patients starting with Dose Cohort A with lenalidomide 15mg PO day 1-14 and pembrolizumab 200mg IV day 1, in cycles of 21 days, until disease progression or toxicity up to 24 months. The number of patients expected to be enrolled in the dose escalation study is 9 (up to 12 patients if unexpected toxicity is observed).

If 0 out of 3 patients at a particular dose level experiences a dose limiting toxicity (DLT) within Cycle 1 of treatment, if in Dose Cohort A (lenalidomide 15mg) dose escalation will proceed to cohort B (lenalidomide 20mg), if in Dose Cohort B, 3 additional patients will be added. If a DLT occurs in 0 of 6 patients enrolled on Dose Cohort B this will be deemed the Maximum Tolerated Dose (MTD).

If a DLT occurs in only 1 out of 6 patients enrolled at a particular dose level, dose escalation will occur, however, if this occurs on Dose Cohort B (lenalidomide 20 mg) or Dose Cohort Z (lenalidomide 10 mg), this will be deemed the Maximum Tolerated Dose (MTD). MTD is defined as the highest dose level at which < 33% of 6 patients experience a DLT.

[figure not shown]
If a DLT occurs in ≥ 2 of 3 patients or ≥ 2 of 6 patients treated on Dose Cohort A (lenalidomide 15mg), there will be a dose de-escalation to Dose Cohort Z (lenalidomide 10 mg).

[figure not shown]
If a DLT occurs in ≥ 2 of 3 patients or ≥ 2 of 6 patients treated on Dose Cohort B (lenalidomide 20 mg) or the preceding dose level will be declared the MTD if there were no more than 1 DLT in this previous cohort.

If a DLT occurs in ≥ 2 of 3 patients or ≥ 2 of 6 patients on Dose Cohort Z (lenalidomide 10mg), the trial will be discontinued and the expanded cohort will not be implemented.

Once the MTD has been determined, 15 additional patients with relapsed refractory HL will be treated in in the Phase II portion of this trial at the MTD.

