5.2 Patient Recruitment and Registration

Patients will be recruited from the Investigators' clinical practices at the Perlmutter Cancer Center (PCC) at NYU Langone Health, Winship Cancer Institute of Emory University, Massachusetts General Hospital (MGH) and Beth Israel Deaconess Medical Center of MGH in Boston, MA. Prior to study entry, a patient's eligibility must be approved in writing by the NYU Clinical Trials Office.

Target accrual for this study is 26-29 patients. Prospective subjects will receive detailed information regarding this study; its investigational nature, required study procedures, alternative treatments, risks and potential benefits of the study. All questions will be answered by the PI and/or qualified research personnel.

The Principal Investigator will:

1. Obtain signed and dated informed consent from the potential subject before any study specific procedures are performed.

2. Determine patient eligibility. (See Section 5.1.2 and 5.1.3)
3. Submit registration to NYU Langone Health Perlmutter Cancer Center Clinical Trials Office (CTO)
4. Receive registration confirmation from the designated CTO staff member at NYU Perlmutter Cancer Center CTO, including a unique study identification number assigned to the patient, which will be distributed to the study team upon registration of the patient.

Enrollment in the study requires that all inclusion and exclusion criteria have been met. Enrollment occurs upon confirmation of registration from the NYU Langone Health Perlmutter Cancer Center (PCC) Clinical Trials Office (CTO). The following materials must be submitted to the research coordinator for registration:

1. Complete signed and dated informed consent form
2. Complete signed and dated eligibility checklist
3. All supporting documentation verifying each criterion has been met

Registration will occur within 48 hours of research coordinator receipt of all of the above documents. A written confirmation of enrollment including a unique study identification number assigned by the research coordinator will be disbursed to the study team upon registration. The patient will not be identified by name. This is the point, at which, the patient is considered accrued on study.

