6.2.2.6 Tumor Imaging and Assessment of Disease

Assessment of lymphoma response (CR, PR or SD) and disease progression will be evaluated according to the Revised Response Criteria for Malignant Lymphoma²⁴. A full IV contrast CT scan combined with a PET scan is preferred for baseline evaluation, interim evaluation (q 12 weeks per standard of care), and at the completion of study. Overall response will be measured for all patients who complete one cycle of treatment. Kaplan-Meier methodology will be used to estimate median PFS and OS.

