7.0 STATISTICAL ANALYSIS PLAN

7.1 Phase I Statistical Analysis Plan

The primary objective of the Phase I portion of this trial is to identify the MTD (Phase II dose) which is the dose at which the estimated proportion of patients with DLTs is less than 0.33. The standard 3+3 design is employed. Patients will be treated in cohorts of 3 patients starting with Dose Cohort A with lenalidomide 15mg PO day 1-14 and pembrolizumab 200mg IV day 1, in cycles of 21 days, until disease progression or toxicity up to 24 months. The number of patients expected to be enrolled in the dose escalation study is 9 (up to 12 patients if unexpected toxicity is observed).

If 0 out of 3 patients at a particular dose level experiences a dose limiting toxicity (DLT) within Cycle 1 of treatment, if in Dose Cohort A (lenalidomide 15mg) dose escalation will proceed to cohort B (lenalidomide 20mg), if in Dose Cohort B, 3 additional patients will be added. If a DLT occurs in 0 of 6 patients enrolled on Dose Cohort B this will be deemed the Maximum Tolerated Dose (MTD).

If a DLT occurs in only 1 out of 6 patients enrolled at a particular dose level, dose escalation will occur, however, if this occurs on Dose Cohort B (lenalidomide 20 mg) or Dose Cohort Z (lenalidomide 10 mg), this will be deemed the Maximum Tolerated Dose (MTD). MTD is defined as the highest dose level at which < 33% of 6 patients experience a DLT.

If a DLT occurs in ≥ 2 of 3 patients or ≥ 2 of 6 patients treated on Dose Cohort A (lenalidomide 15mg), there will be a dose de-escalation to Dose Cohort Z (lenalidomide 10 mg).

If a DLT occurs in ≥ 2 of 3 patients or ≥ 2 of 6 patients treated on Dose Cohort B (lenalidomide 20 mg) or the preceding dose level will be declared the MTD if there were no more than 1 DLT in this previous cohort.

If a DLT occurs in ≥ 2 of 3 patients or ≥ 2 of 6 patients on Dose Cohort Z (lenalidomide 10mg), the trial will be discontinued and the expanded cohort will not be implemented.

Once the MTD has been determined, 17 additional patients with relapsed refractory HL will be treated in in the Phase II portion of this trial at the MTD.

While clinical benefit rates and other outcome rates for each dose cohort will be estimated, all of the summary of patient outcomes is descriptive.

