7.2 Phase II Statistical Analysis Plan

This is an open label single arm Phase II study to test the hypothesis that the CR rate is less than or equal to 20% versus the alternative hypothesis that the CR rate is greater than or equal to 50%.

Our sample size estimate is based on our primary hypothesis that evaluates CR rate in the HL cohort. One-sided binomial tests will be used to assess these changes. Given a baseline CR of 21% for single agent pembrolizumab in relapsed HL, we hypothesize that combination of lenalidomide and pembrolizumab will have a CR rate of 50% or greater for the combination at a significance level of 0.05 with 80% power (PASS, 2008).

With 17 patients entered into this trial, with 83% power and alpha of 0.04, we can reject the null hypothesis if 6 or fewer responses are observed.

Patient and disease characteristics will be summarized at baseline using descriptive statistics (means, medians, quartiles, standard deviations, etc.) and graphical displays including boxplots for continuous variables and frequency distributions for qualitative variables.

The complete response rate will be estimated with exact 95% confidence intervals. Other secondary response measures will be summarized using frequency distributions. Distributions of dose and time on treatment will also be summarized. Time to failure will be estimated using Kaplan Meier methods (failures include progression or death, death). Descriptive summaries of response duration and transfusion independence duration will also be summarized using Kaplan Meier methods ²⁵.

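### Section 2.1 sets Phase 2 at 15 patients, but the trial summary, the SAP and the accrual totals are built on 17

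*Combined protocol and SAP*

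**What the plan says.** The protocol gives two sizes for the Phase 2 Hodgkin lymphoma cohort.

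- Section 2.1 (Trial Design): "Once the MTD has been determined, 15 additional patients with relapsed refractory HL will be treated".
- Section 1.0 (Trial Summary): "Phase 2: 17 patients with RR HL", with a trial total of "26 (up to 29 if unexpected toxicity" patients.
- Section 5.2 (Patient Recruitment and Registration): "Target accrual for this study is 26-29 patients".
- SAP 7.1, in what is otherwise the same sentence as Section 2.1: "Once the MTD has been determined, 17 additional patients with relapsed refractory HL will be treated".
- SAP 7.2, where the test is sized: "With 17 patients entered into this trial, with 83% power and alpha of 0.04".

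Phase 1 is put at 9 patients, or up to 12 with unexpected toxicity, in Sections 1.0, 2.1 and 7.1 alike.

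**The concern.** Section 2.1 defines the design, so it is where a reader would look for the cohort size. It is current text, not part of the summary of changes. Nothing in the documents explains 15 as, for example, an evaluable subset of 17. The sentence recurs in SAP 7.1 with only the number different, which suggests that one copy was updated and the other was not; that is an inference.

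The practical risk is that Phase 2 accrual is closed at 15, or that the pre-specified size is disputed afterwards. The question for the calculation is whether the design could absorb the loss of two patients.

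**Working it through.** **Inputs.** All from SAP 7.2 unless noted: null CR rate 20% (a baseline of 21% is also cited), alternative 50%, one-sided binomial test, design targets alpha 0.05 and power 80%, achieved values at 17 patients alpha 0.04 and power 83%. Phase 1 size 9 or 12, and totals 26 or 29, from Section 1.0.

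**Step 1: totals.**

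- With 17: 9 + 17 = 26 and 12 + 17 = 29. Both match Section 1.0.
- With 15: 9 + 15 = 24 and 12 + 15 = 27. Neither matches.

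**Step 2: reproduce the SAP's alpha and power.** For n patients and rejection at r or more CRs, with X binomial:

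- alpha = P(X ≥ r | n, 0.20)
- power = P(X ≥ r | n, 0.50)

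At n = 17 and r = 7:

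- alpha = 0.0377, which rounds to 0.04.
- power = 109,294 / 2^17 = 109,294 / 131,072 = 0.8338, which rounds to 83%.

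The cut-off r = 7 is inferred. SAP 7.2 says "we can reject the null hypothesis if 6 or fewer responses are observed". Read literally at n = 17, that rule has probability 0.9623 under a 20% CR rate and 0.1662 under 50%, so it cannot be the rule behind 0.04 and 83%. Its complement, 7 or more, is.

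**Step 3: is 17 the only size that fits?** Across every n from 1 to 100 and every cut-off, with a 20% null, only n = 17 with r = 7 rounds to both 0.04 and 0.83. With a 21% null, no design does.

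**Step 4: what happens at other sizes?**

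| n | Reject at | Alpha, null 20% | Alpha, null 21% | Power at 50% |
|---|---|---|---|---|
| 15 | ≥ 6 | 0.0611 | 0.0748 | 0.8491 |
| 15 | ≥ 7 | 0.0181 | 0.0234 | 0.6964 |
| 16 | ≥ 6 | 0.0817 | 0.0992 | 0.8949 |
| 16 | ≥ 7 | 0.0267 | 0.0342 | 0.7728 |
| 17 | ≥ 6 | 0.1057 | 0.1273 | 0.9283 |
| 17 | ≥ 7 | 0.0377 | 0.0479 | 0.8338 |

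At n = 15, a cut-off of 7 keeps alpha but misses 80% power, and a cut-off of 6 keeps power but exceeds alpha 0.05. A higher cut-off only lowers power further, and a lower one only raises alpha further. The smallest n with alpha at most 0.05 and power at least 0.80 is 17, under either null.

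The power lost by stopping at 15 and keeping the cut-off of 7 is 0.8338 − 0.6964 = 0.1374, about 14 percentage points.

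**The case against.** The strongest reply is that the error is unlikely to do harm. The recruitment section, the trial summary and both SAP sections point to 17, registration runs through one central office, and the data safety monitoring committee reviews accrual every quarter. An attentive team would probably enrol 17. This stands, and it is why the point should be fixed but does not undermine the design.

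The loss of 14 points is also conditional. It needs accrual to stop at 15 and a cut-off of 7 to be applied, and that cut-off is not printed anywhere. With a cut-off of 6, power at 15 would be 0.849, slightly above plan, and the cost would be an alpha of 0.061. This stands too: the size of the harm depends on the scenario. Under either cut-off, however, one of the protocol's own two targets is missed.

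Finally, the range of 26 to 29 in Section 5.2 does not settle the matter alone, because 24 to 27 overlaps it. That is correct. The decisive evidence is Section 1.0, which gives 26 for the expected case and 29 for unexpected toxicity, the same two cases for which it gives 9 and 12 Phase 1 patients.

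None of these arguments supports 15 as the intended number.

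**Conclusion.** The concern holds. Section 2.1 states the wrong Phase 2 sample size, and 17 is the intended figure. The direct contradiction and the totals show this without any assumption about the rejection rule. The alpha and power figures confirm it, given an exact one-sided binomial test of 20% against 50% with rejection at 7 or more CRs.

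The design has no slack: even 16 patients with a cut-off of 7 gives power of only 0.773. If accrual did stop at 15, the test would have either power 0.696 at alpha 0.018, or alpha 0.061 at power 0.849 (20% null). The safeguards elsewhere in the protocol make that outcome avoidable, so this is a correction that should be made rather than a flaw in the planned test.

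**What to change.** In Section 2.1, change 15 to 17 so that it agrees with Sections 1.0, 7.1 and 7.2. The cost is one number in a protocol amendment. Planned accrual of 26 to 29, alpha and power are unchanged, and no treatment rule is affected. The reversed rejection rule in SAP 7.2 needs its own correction; changing 15 to 17 does not repair it.

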2.2 Trial Diagram

3.0 OBJECTIVE(S) & HYPOTHESES

3.1 Primary Objective(s) & Hypothesis

Objective:

Phase 1: To determine the maximum tolerated dose (MTD) and dose limiting toxicities (DLT) of the combination of pembrolizumab and lenalidomide, in patients with RR HL and B cell NHL.

Phase 2: To estimate the overall response rate (ORR), (complete response rate (CR) and partial response rate (PR)) in patients with RR HL

Hypothesis:

Phase 1: We hypothesize that the novel immune platform of pembrolizumab and lenalidomide, will be safe and well tolerated in patients with RR HL and NHL

Phase 2: We hypothesize that the novel immune platform of pembrolizumab and lenalidomide will result in a CR rate of 50% in patients with RR HL.

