3.2 Secondary Objective(s) & Hypothesis

Objectives:

Phase 1: To estimate the ORR, (CR, PR), SD and progression free survival (PFS) for the combination within and across dose levels of lenalidomide

Phase 2: To estimate clinical benefit (including SD), the PFS and duration of response (DOR), for the combination. To confirm the safety of the combination.

Hypothesis:

Phase 1: We hypothesize that the novel immune platform of pembrolizumab and lenalidomide, will be active in RR HL and NHL patients.

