4.2 Rationale

4.2.1 Rationale for the Trial and Selected Subject Population

Checkpoint inhibitory drugs, such as pembrolizumab, targeting the PD-1/PD- L1 signaling pathway have been shown to promote marked antitumor immunity in patients with HL and in a subset of patients with NHL. Despite its activity and the high ORR seen in heavily pretreated patients with HL, pembrolizumab as single agent has shown only a modest CR rate of 21%.

We hypothesize that the combination of pembrolizumab with lenalidomide, an agent with complimentary immune stimulatory activity, and non-overlapping toxicity, might enhance its

therapeutic efficacy in patients with relapsed refractory HL. This novel treatment platform, which is chemotherapy free, may be highly effective for long term disease control as maintenance strategy or remission induction, and may have a role in earlier line management of frail elderly patients with relapsed disease, or who are unable to tolerate standard chemotherapy.

If this treatment strategy is safe and effective, this will provide the justification to bring this strategy in larger scale randomized trials, or to consider triplet combinations with rituximab which may ultimately demonstrate the significance of this platform in the management of multiple B cell lymphoma subtypes.

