4.2.3 Rationale for Endpoints

4.2.3.1 Efficacy Endpoints

In the phase 1 part of the study, the primary endpoints are safety and tolerability of the combination of pembrolizumab and lenalidomide, with determination of the MTD of lenalidomide in combination.

In the phase 2 portion of the study, the primary endpoints are overall activity assessment (CR, ORR, and PR) and of the combination of pembrolizumab with the MTD of lenalidomide in patients with RR HL.

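### Sections 3.1 and 4.2.3.1 make ORR primary in Phase 2, but Section 7.2 gives a test and an exact interval to CR only, so ORR's status is contradictory

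*Combined protocol and SAP*

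**What the plan says.** Two sections give ORR primary status in Phase 2:

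- Section 3.1, objective: "Phase 2: To estimate the overall response rate (ORR), (complete response rate (CR) and partial response rate (PR".
- Section 4.2.3.1: "the primary endpoints are overall activity assessment (CR, ORR, and PR". The three rates are given in no order.

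The hypothesis and the analysis concern CR:

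- Section 3.1, hypothesis: the combination "will result in a CR rate of 50% in patients with RR HL".
- Section 4.2.1, rationale: "pembrolizumab as single agent has shown only a modest CR rate of 21" percent.
- Section 7.2: the study is "to test the hypothesis that the CR rate is less than or equal to 20" percent, against 50% or more, and "Our sample size estimate is based on our primary hypothesis that evaluates CR rate in the HL cohort". The exact 95% confidence interval is promised for the complete response rate only. The remaining response measures are called secondary and are to be shown as frequency distributions. ORR is not named.
- Section 7.2, decision rule: "we can reject the null hypothesis if 6 or fewer responses are observed".

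Two other places bear on ORR. Section 3.2 reads "Phase 2: To estimate clinical benefit (including SD), the PFS and duration of response (DOR), for the combination" and adds confirmation of safety; ORR appears there as a secondary objective for Phase 1 but not for Phase 2. Section 6.2.2.6 says that overall response is measured in patients who finish one cycle.

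**The concern.** The objective and endpoint sections do not give ORR the same status as the analysis section. In Sections 3.1 and 4.2.3.1 it is primary. In Section 7.2 it can only fall among the other response measures, which are called secondary. In the Phase 2 part of Section 3.2 it is absent.

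The Section 3.1 objective is one of estimation, and the main thing to plan for an estimated rate is how its uncertainty will be shown. The plan does this for CR and not for the rate named first in the objective. At the reporting stage, the plan would allow ORR to be presented either as a primary result or as a descriptive secondary one.

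The decision rule adds a smaller gap. In a document that also labels overall response primary, it counts responses without saying complete responses.

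**Working it through.** **1. Which endpoint do the stated figures belong to?**

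Inputs from Section 7.2: n = 17, null CR rate 20%, alternative 50%, one-sided binomial test, stated power 83% and alpha 0.04. (Section 2.1 gives 15 Phase 2 patients. I use 17, as in Sections 1.0, 7.1 and 7.2; that difference is a separate matter.)

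For rejection at r or more complete responses:

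P(X ≥ r) = Σ (k = r to 17) C(17, k) p^k (1 − p)^(17−k)

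| Reject if X is at least | Alpha at 20% | Power at 50% |
|---|---|---|
| 6 | 0.1057 | 0.9283 |
| 7 | 0.0377 | 0.8338 |
| 8 | 0.0109 | 0.6855 |

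Only the cutoff of 7 gives 0.04 and 83% after rounding. The power can be checked by hand: at 50%, P(X ≤ 6) = (1 + 17 + 136 + 680 + 2,380 + 6,188 + 12,376) / 131,072 = 21,778 / 131,072 = 0.1662, and 1 − 0.1662 = 0.8338. At the cited single-agent rate of 21%, the cutoff of 7 gives alpha 0.0479, still below 0.05. The plan's figures are therefore those of a CR test.

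**2. What does the printed rule do?**

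Rejecting at 6 or fewer has probability 1 − 0.0377 = 0.9623 at a CR rate of 20% and 0.1662 at 50%. The printed rule rejects almost always under the null and seldom under the alternative. Six or fewer is the region in which the null is *not* rejected.

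**3. What status does ORR have, section by section?**

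| Section | Status of ORR in Phase 2 |
|---|---|
| 3.1, objective | Primary, to be estimated |
| 3.1, hypothesis | Not mentioned; CR only |
| 3.2 | Not listed |
| 4.2.3.1 | Primary, beside CR and PR |
| 6.2.2.6 | Population given; no interval, no role |
| 7.2 | Not named; by default secondary, frequency distribution |

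The entries for 3.1 (objective) and 4.2.3.1 cannot both stand with the entry for 7.2.

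**4. What would the missing sentence produce, and on which denominator?**

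The exact interval for x of n has lower limit the 0.025 quantile of Beta(x, n − x + 1) and upper limit the 0.975 quantile of Beta(x + 1, n − x). For 11/17 (65%) it is 38% to 86%. This only illustrates the output. The width comes from having 17 patients and does not measure the defect.

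The denominator also needs stating. Section 6.2.2.6 leaves out patients who do not finish one cycle, and Section 5.8 does not provide for replacing those who leave early because of progression, lymphoma-related death or treatment toxicity. The ORR denominator may therefore be below 17. If, as an assumption, two patients were left out in this way, 11 responders would be 11/15 = 73% rather than 11/17 = 65%.

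**The case against.** The strongest reply is that the plan already puts CR first. Section 7.2 calls CR the primary hypothesis, Section 3.1 has only one Phase 2 hypothesis and it is on CR, and CR has the only null, alternative, sample size and interval. That stands. A reader might infer from Sections 3.1 and 4.2.3.1 that the tested endpoint is undefined; the documents do not support that.

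A reader might also infer that ORR has no planned analysis. That goes too far. The frequency distributions in Section 7.2 can cover ORR, and Section 6.2.2.6 gives response criteria, timing and a population. What is missing is an interval and a status that agrees across sections. An exact interval can be computed later from the reported counts, so no information is lost.

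A third tempting reading is that the word responses in the rule means CR plus PR. No passage directs that count, the only null is on CR, and the stated alpha and power match CR rates. The missing word is a drafting gap and not evidence of a test on ORR.

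Finally, estimating several response rates beside one tested rate is not an error, and an estimation objective needs no null or power. I ask for neither. None of this removes the conflict over ORR's status, or the absence of an interval for the rate in the primary objective.

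**Conclusion.** The point holds as an inconsistency that should be fixed. ORR is primary in two sections, secondary by default in Section 7.2 and absent from the Phase 2 list in Section 3.2, and the primary estimation objective has no interval for it. CR is the tested endpoint: 7 or more of 17 gives alpha 0.038 at 20% and power 0.83 at 50%, which are the plan's own figures.

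The size is limited. The CR question, the 17 patients and the data collected are unaffected. What is at stake is which result may be called primary and whether ORR is reported with its uncertainty. The printed rule is a plain error in the same section: it points the wrong way (rejection probability 0.962 at 20%, 0.166 at 50%) and does not name complete responses.

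This rests on taking 17 as the Phase 2 number and on reading the general sentence on other response measures in Section 7.2 as including ORR. If that sentence does not include ORR, the conflict of labels with Section 7.2 goes, but Section 7.2 then says nothing about how ORR is summarised.

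**What to change.** - In Sections 3.1, 4.2.3.1 and 7.2, name CR rate as the single tested Phase 2 primary endpoint.
- In the same sections, label ORR and PR rate as estimation only, each with an exact 95% confidence interval and no hypothesis test. ORR may stay in Section 3.1 under that label or move to the Phase 2 list in Section 3.2.
- In Section 7.2, state the denominator for these rates and make it agree with Section 6.2.2.6, noting that it may be below 17.
- In Section 7.2, rewrite the rule so that the null is rejected if 7 or more complete responses are seen among 17 patients (alpha 0.038 at 20%, power 0.83 at 50%).

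The cost is wording in three sections, plus Section 3.2 if ORR moves and Section 6.2.2.6 if the denominator is settled there. Sample size, data collection and the CR test stay as they are. The downside is that ORR may lose its primary label.
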